8.1.6 Allowed Medications

8.1.6.1 Antimicrobial Agents

All patients will receive one or more antimicrobial drugs used as SoC to treat the primary or subsequent infections. Antimicrobial agents include antibacterial, anti-fungal, anti-viral and anti-parasitic drugs. Topically applied antimicrobial agents should be included. Any other medications whether drugs or biologics used to treat the patient should be identified as non-antimicrobial medications.

Each antimicrobial agent will be identified by its generic or trade name and reported in the eCRF. Information should include the dose, dosing frequency, route of administration, duration (start and stop times and dates), and reason for administration (to treat primary or secondary infection or for surgical prophylaxis).

8.1.6.2 Non-antimicrobial Medications

Contrast-enhancing agents used to evaluate patients for abdominal infection (or other complications following study entry) are allowed but should be captured as described below for other non-antimicrobial drugs.

Non-antimicrobial (ancillary) drugs administered from the time of patient screening until end of study will be recorded in the eCRF. Information to be collected should include generic or trade name, route of administration, duration (start and stop dates) and reason for administration. A list of medications that are not required to be captured in the ancillary medication eCRF is provided in the Study Procedure Manual.

8.2 Study Medication Compliance

Compliance will be monitored by recording the total volume of each investigational agent actually delivered to each study patient.

8.3 Precautions and Overdose

8.3.1 Study Drug - Reltecimod

8.3.1.1 Precautions

Currently available safety information does not require any special precautions to be exercised during treatment with Reltecimod. Analysis of safety data collected in Reltecimod Phase 1 and 2 studies, did not reveal AEs that were determined as related to Reltecimod (including possibly, probably and definitely related to study drug). In animal toxicology studies no target organs were identified.

8.3.2 Placebo Comparator

No known or expected adverse reactions are associated with pyrogen-free, preservative-free, physiologic saline.

8.3.2.1 Precautions

None for placebo comparator.

9. STUDY PROCEDURES

9.1 Informed Consent

The ICF is in compliance with ICH GCP Guidelines, and in accordance with the Federal Regulations as detailed in 21 CFR §50.25 and the Declaration of Helsinki.

Prior to entering the study, the Investigator/designee will explain the nature of the study to each patient or LAR its purpose, expected duration, alternative forms of therapy available and the benefits and risks of study participation. After this explanation and before entering the study, the patient or LAR will read and understand the ICF and voluntarily sign a consent form in the presence of the Investigator/designee. LAR may utilize phone/fax/email/e-consent or written consent as allowed by the local institutional policies and procedures.

The patient will be given a copy of the signed/dated ICF.

9.2 Clinical and Laboratory Procedures

9.2.1 Start of Drug Administration Clock

The IV drug administration clock of maximal 6 hours starts once the patient is diagnosed with Stage 2 or 3 AKI as established at the study site, only after the decision is made by the attending surgeon at the study site for a surgical or interventional radiology procedure for the abdominal infection or after confirmed diagnosis of abdominal infection has been established by a surgical or interventional radiology procedure; or after surgical confirmation of NSTI as described in the inclusion criteria (Section 76.1).

9.2.2 Inclusion/Exclusion Criteria

The inclusion and exclusion criteria are specified in Sections 6.1 and 6.2. These criteria determine patient eligibility for recruitment. All patients must be evaluated for the presence of all inclusion criteria and the absence of all exclusion criteria before they are eligible to receive study drug.

9.2.3 Medical and Surgical History

A complete medical history identifying clinically relevant past medical and surgical conditions and active medical or surgical conditions will be reported on the Medical History eCRF. All chronic medications will be identified and characterized by trade or generic name, route of administration as well as reason for use from 14 days prior to study drug administration to Day 28.

Baseline signs and symptoms, defined as pre-emergent adverse events, should be captured on the Baseline Signs and Symptoms eCRF form.

9.2.4 Physical Examinations

Physical examination will include a clinically appropriate examination of vital organ systems. These should include at minimum cardiovascular, respiratory, abdomen, extremities, and neurologic body systems. Physical exams do not need to be performed if subject is being evaluated by a visiting nursing service as an outpatient.

9.2.4.1 Interim Physical Examinations (Symptom-driven)

Interim PE will be targeted to include clinically appropriate examination of specific organ systems based on patient related signs and symptoms.

9.2.5 Concomitant Medications

All concomitant medications, antimicrobial & non-antimicrobial, (with the exception of over the counter medications (unless nephrotoxic), vitamins, laxatives, intravenous fluid and electrolyte replacement, parenteral nutrition, topical medications and other selected medications as described in the Study Procedure Manual) will be entered into the eCRF and identified by their generic or trade name.

Information about antimicrobial medications, immunosuppressants, and nephrotoxic drugs should include the dose, dosing frequency, route of administration, duration (start and stop times and dates), and reason for administration (to treat primary or secondary infection or for surgical prophylaxis).

Information to be collected about non-antimicrobial medications, immunosuppressants, or nephrotoxic drugs should include generic or trade name, route of administration, duration (start and stop dates) and reason for administration.

Timing and adequacy of antibiotic therapy (based on institutional guidelines, baseline pathogens and antimicrobial sensitivity) will be reviewed by the Principle Investigator.

9.2.6 Abdominal Infection Type

The cause and type of the abdominal process (e.g. complicated appendicitis or diverticulitis, peritonitis due to perforation of small or large intestine, post-traumatic peritonitis) causing peritonitis and abdominal infection along with factors predisposing to abdominal infection will be captured. The date and time of diagnosis of abdominal infection and type of surgical or interventional procedure(s) to establish source control through Day 14 will be recorded.

9.2.7 NSTI Infection Site

Details of the NSTI will be recorded on the eCRF and include: “clinical characteristics” (as a specific subset of NSTI) at the time of enrollment; location of primary infection; extension of infection; date of onset of symptoms, identified predisposing factors (trauma, surgery, IV drug use, comorbidities such as diabetes or obesity, bites; prior surgical procedures related to the etiology of NSTI; prior surgical procedures for the treatment of the primary infection site and whether those procedures were considered adequate; antimicrobial use from the date of onset of current illness (may predate diagnosis of NSTI); description of the NSTI lesion; date and time of surgical intervention for NSTI and surface area of NSTI debridement (when available).

The primary NSTI infection site will be described in detail. Any visible wound or drainage will be characterized as to amount, and cellular composition (purulent, sero-sanguineous, sanguineous, other). Tissue edema, focal pain and presence of subcutaneous crepitus, the presence of tissue discoloration, blisters, bullae or necrosis will be identified. The extent of progression of necrosis as well as the need for repeated surgical procedures will be documented by the Investigator.

9.2.8 Acute Kidney Injury

During screening, it will be recorded whether the patient presented with Stage 2 or 3 AKI, or developed Stage 2 or 3 AKI within 48 hours after the suspected or confirmed diagnosis of abdominal infection, or surgical confirmation of NSTI. If a reference (baseline) serum creatinine value(s) is/are available from the past 12 months, the reference serum creatinine value(s) and date(s) obtained will be entered. If the subject does not have a reference serum creatinine value, it will be noted if the serum creatinine is ≥ 2.0 fold normal for age, race, and gender, and the length of the largest kidney by CT or renal ultrasound.

The stage of AKI (Stage 2 or 3) and how AKI was diagnosed (serum creatinine or urine output or both) will be recorded. The screening creatinine value prior to study drug administration as well as additional creatinine values from presentation or around (before) time of diagnosis of abdominal infection or NSTI should be entered. Urine output should be computed from presentation or around (before) time of diagnosis of abdominal infection or NSTI after accurate urine output is recorded. After study drug administration, urine output is collected while subject is in the ICU or step-down unit (or equivalent) with or without a Foley catheter in place through Day 7.

If receiving RRT, then the type of RRT and net fluid removed per RRT session will be collected through Day 28. Additional renal imaging or renal procedures (e.g., renal biopsy) performed as part of SoC through Day 28 will be entered in the eCRF.

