5.3 Exploratory Objectives

- To compare the primary endpoint at Day 90 between the Reltecimod- and placebo-treated patients
- To compare the rates of improvement in durable loss of renal function (defined as alive, free of dialysis, and improvement leading to a lower AKI stage but no better than Stage 1 AKI) at Days 14, 28, and 90, between the Reltecimod- and placebo-treated patients
- To compare the distributions of acute kidney disease (AKD) stages (AKD 0, 1, 2, 3, and 3F) at Days 14 and 28 between the Reltecimod- and placebo-treated patients
- To conduct an exploratory evaluation of the incidence of CKD at Day 90
- To conduct an exploratory evaluation of survival status at Day 90 in the Reltecimod- and placebo-treated patients
- To conduct an exploratory evaluation of the primary endpoint by baseline pathogen
- To conduct an exploratory evaluation of RRT use (i.e., type of RRT)
- To evaluate the immunogenicity of Reltecimod
- To conduct an exploratory evaluation of plasma and urinary biomarkers in patients with AKI
- To conduct an exploratory evaluation of blood leukocyte transcriptome (RNA expression) profiling in patients with SA-AKI and compare genomic profile in patients treated with Reltecimod versus placebo
- To define potential surrogate biomarkers (systemic) that exhibit change from

baseline due to treatment with Reltecimod

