- Assess lesion status if NSTI (healing/progression/significant change in appearance) if accessible for visible assessment at time of debridement or routine dressing change
- Record Survival

Visit 8 (Day 21 [±1 day])

- Collection of AEs/SAEs, including secondary infections
- Collect data on additional amputations if NSTI
- Collect data on acute RRT
- Record additional relevant procedures related to the kidney (e.g., renal biopsy)
- Record any imaging that evaluates the kidney
- Concomitant medications
- Critical care parameters (dates and times of assisted ventilation, vasopressor use, ICU /hospital stay)
- Record any hospital re-admissions (if previously discharged for original sepsis-related hospitalization)
- Vital Signs (to be taken during the morning tests if still hospitalized)
- Serum creatinine
- Record Survival

Visit 9 (Day 29 [+3 days])

- Weight
- Collection of AEs/SAEs, including secondary infections

- Collect data on acute RRT
- Record additional relevant procedures related to the kidney (e.g., renal biopsy)
- Record any imaging that evaluates the kidney
- Collect data on additional amputations if NSTI
- Concomitant medications
- Critical care parameters (dates and times of assisted ventilation, vasopressor use, ICU /hospital stay)
- Vital signs (to be taken during the morning tests if still hospitalized)
- Serum creatinine and albumin
- CBC with differential and platelet count
- Standard CRP
- Spot urine for albumin to creatinine ratio
- Collect blood for serum for storage (immunogenicity testing)
- Record any hospital re-admissions (if previously discharged for original sepsis-related hospitalization)
- Record Survival

All efforts should be made to collect these data, especially laboratory data, with Day 28 being the primary endpoint, but in case parameters cannot be collected, phone follow-up will be performed, and information that could be collected over the phone will apply.

Visit 10 (3 to 21 Days after Visit 9)

- Serum creatinine

Visit 11 (Day 90 [+5 days])

The 3-month visit is a follow-up visit to assess the long-term health condition of the patients including assessment of

- Serum creatinine
- Spot urine for albumin to creatinine ratio
- Serum for storage (immunogenicity test)
- Record survival
- Record any hospital readmission(s) within 30 days of discharge from original sepsis-related hospitalization.

Follow-up of Patients

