3.10.6 Additional Processing Details

Based on experience gained through processing of AKI endpoints in the recently completed ATB-202 study, the following data processing convention will be employed.

- To account for renal replacement therapy (RRT), the exact dates on which the patient is on dialysis will be determined and compared to the exact date on which the labs were drawn for the creatinine sample. If the sample was drawn within 2 days from RRT start then it was excluded from all analyses.
- If the reference creatinine is greater than 1.4, then all available creatinine values obtained on Day 10 and after, including unscheduled visits, will be evaluated. If the maximum is 1.5x the minimum, then the reference creatinine is replaced by the MDRD.
- LOCF will be used for missing Day 14 creatinine starting from Day 10.
- LOCF will be used for missing Day 28 creatinine starting from Day 7.

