4.2 Secondary Effectiveness Endpoints

The secondary effectiveness endpoints for this study are:

- Freedom from durable loss of renal function at Day 14
- Freedom from durable loss of renal function at Day 90

Reference creatinine values, baseline AKI stage and percentage loss of eGFR at Days 14 and 90 will be determined through algorithmic determination (see details above). Percentage loss of eGFR determined algorithmically will be based on a comparison of eGFR at screening compared to an algorithmically determined reference creatinine value

- Resolution of organ dysfunction (organ resolution is defined as having a total mSOFA score of ≤ 1) at Day 14
- Resolution of specific organ dysfunction (defined as having an individual organ mSOFA score of ≤ 1) at Day 14
- Critical care and hospital stay parameters
 - Hospital length of stay
 - ICU length of stay
 - ICU-free days in 28 days
 - Days on ventilator
 - Ventilator free days in 28 days
 - Vasopressor days
 - Vasopressor free days in 28 days
 - Discharge status

- Patient survival at Days 14, 28 and 90.
- Presentation of Stages 1, 2, or 3 AKI (using the KDIGO criteria)
- **Stratifications involving Day 14 mSOFA \leq 1 vs Day 14 mSOFA \geq 2**
 - Compare critical care between Day 14 mSOFA \leq 1 vs Day 14 mSOFA \geq 2
 - Compare dose groups in those with Day 14 mSOFA \leq 1
 - Compare dose groups in those with Day 14 mSOFA \geq 2
- Among patients presenting with cardiovascular failure (shock), dose group predicting Day 14 mSOFA \leq 1
- Survival to Day 90 as a function of *freedom from durable loss of renal function at 28* (overall and by dose group)

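### The readable visit lists record no dialysis data after Visit 9, although the Day 90 endpoint requires freedom from dialysis; separately, the SAP's Day 90 eGFR formula uses the Day 14 creatinine

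*Protocol*

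**What the plan says.** **Endpoint.** Protocol 5.3 lists as exploratory "To compare the primary endpoint at Day 90 between the Reltecimod- and placebo-treated patients". Under Protocol 5.1 that endpoint means alive, free of dialysis and less than a 37% loss of eGFR from reference. SAP 4.2 makes "Freedom from durable loss of renal function at Day 90" a secondary endpoint, and SAP 5.3 gives it the same analysis as the primary. The improvement measure in Protocol 10.3, also assessed at Day 90, requires freedom from dialysis too.

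**Collection.** In Protocol 7.3 the item "Collect data on acute RRT" appears at every visit from Visit 1 to Visit 9, and in the Days 4 to 6 list. Visit 10 lists serum creatinine only. Visit 11 is introduced with "The 3-month visit is a follow-up visit to assess the long-term health condition of the patients including assessment of" and then names creatinine, spot urine albumin/creatinine, immunogenicity serum, survival, and readmissions within 30 days of discharge. Protocol 9.2.8 says "If receiving RRT, then the type of RRT and net fluid removed per RRT session will be collected through Day 28".

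**Analysis.** SAP 3.10.6 says that "the exact dates on which the patient is on dialysis will be determined" and compared with the date of the creatinine draw. A sample drawn within 2 days of RRT start is excluded from all analyses. SAP 3.10.5 introduces its formula as a conversion of the Day 90 creatinine, but the formula contains the Day 14 creatinine. It writes out only the eGFR criterion for Day 90.

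**The concern.** One of the three components of the Day 90 endpoint has no visit at which the readable text asks for it. The SAP's rule for removing dialysis-affected creatinines also needs dates that are not specified for collection after Visit 9. Dialysis lowers serum creatinine, so a patient who still depends on it at Day 90 can look recovered on the laboratory value alone. Such patients have the worst renal outcome among survivors, and the Day 90 endpoint exists to show long-term renal outcome. The Day 90 CKD analysis in SAP 4.3 and 9.4 also uses eGFR and would take in the same creatinines.

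**Working it through.** No planned figure rests on this point, so there is none to reproduce. The check sets what is needed beside what is collected, then works out how far the eGFR criterion alone could catch a patient on dialysis.

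**Needed against collected**

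| Item | Needed by | Listed through Visit 9 | Listed at Visit 10 | Listed at Visit 11 |
|---|---|---|---|---|
| Survival | Day 90 endpoint | yes | no | yes |
| Creatinine | Day 90 endpoint | yes | yes | yes |
| Dialysis status | Day 90 endpoint | yes | no | no |
| RRT dates | SAP 3.10.6 | yes | no | no |

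Visit 10 matters because Protocol 12.11.2 uses it to confirm creatinine values.

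**The exclusion rule.** The phrase about RRT start can be read in two ways. If it means a dialysis session, the rule needs session dates after Visit 9, which are not specified. If it means the start of therapy, the date is on record for anyone who began by Visit 9. But a patient on dialysis since the first month gives a Day 90 sample far more than 2 days after that start, so the rule would keep the sample. On the second reading, dialysis status is the only safeguard for that patient.

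**What the eGFR criterion can catch.** In the SAP formula eGFR is proportional to creatinine to the power -1.154. Sex and race factors cancel, and age is taken as unchanged.

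- A 37% loss leaves 0.63 of reference eGFR.
- Creatinine ratio at the limit: (1/0.63)^(1/1.154) = 1.492.
- Example (assumed values): reference 1.2 mg/dL gives a limit of 1.2 × 1.492 = 1.79 mg/dL. A sample of 1.7 mg/dL after a session gives 1.7/1.2 = 1.417, below 1.492, so the eGFR criterion is met.

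The 1.492 limit follows the endpoint definition, which compares with reference. The formula printed in SAP 3.10.5 compares with screening eGFR. On that formula a patient screened at 2 times reference fails only at 2 × 1.492 = 2.98 times reference, and one screened at 3 times only at 3 × 1.492 = 4.48 times. The eGFR criterion would then catch even fewer dialysis-dependent survivors.

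**Possible size.** The documents give no Day 90 dialysis rate. Assume that 2% to 10% of a 60-patient arm are on dialysis at Day 90 and wrongly counted as successes: 0.02 × 60 = 1.2 and 0.10 × 60 = 6, so about 1 to 6 patients per arm. Each one moves that arm's rate by 1/60 = 1.7 percentage points. Equal numbers in both arms leave the difference unchanged. With 6 on placebo and 3 on active, the difference shrinks by 3/60 = 5 points, against the drug.

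**The formula.** With the Day 14 creatinine in place, Day 90 eGFR equals Day 14 eGFR for every patient, since all other terms are the same.

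**The case against.** The strongest reply is that the text does not prove the data are missing.

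- The RRT row in Protocol Appendix A exists, but its time bar cannot be read. The same holds for the SAP's schedule. This is evidence for neither side. If the bar runs to Day 90, it disagrees with 7.3 and 9.2.8, and the three must be reconciled.
- The Visit 11 list is introduced as including certain items, so it may not be exhaustive. But RRT is named at every earlier visit, which makes its absence here meaningful.
- Protocol 10.4 gives the adjudicators RRT dates with no end day, beside creatinine up to 90 days, and lets them ask for more. This shows that the dates are wanted, not which visit collects them. SAP 4.1 and 4.2 determine eGFR loss by algorithm.
- SAP Appendix 3 lists a Renal Replacement Therapy form and a Month 3 Visit Status form. Their contents are not given.
- Protocol 11.3.2 follows unresolved adverse events to study end, so some patients still on RRT at Day 28 may be tracked. That need not yield session dates or a dialysis status at Day 90.

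A reader might also infer more than the documents support:

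- **That dialysis data stop at Day 28 and the primary endpoint suffers.** Visit 9 still lists RRT collection, and the sentence in 9.2.8 limits only RRT type and net fluid.
- **That affected creatinines can never be identified.** Chart review could recover dates. The gap is in what the plan specifies.
- **That a patient on RRT at Day 28 who later recovers would be counted a failure.** No stated rule carries an open RRT record forward.

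Finally, SAP 3.10.5's own lead-in sentence makes its intent plain, so the Day 14 term is evidently a copying error. It still needs correcting: SAP section 1 puts the SAP above the protocol, and a programmer may code the formula as printed.

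**Conclusion.** The point holds for Day 90. Dialysis status at that visit, and RRT dates after Visit 9, are required by the endpoint and by SAP 3.10.6 but are not specified for collection in the readable text. A dialysis-dependent survivor with a creatinine below about 1.49 times reference could therefore be counted a success. How many patients this concerns cannot be known from the documents; the 1 to 6 per arm above is an assumption, not an estimate. The conclusion also assumes that the unreadable schedule bars and the undescribed forms do not already cover Day 90.

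The components of the Day 28 primary endpoint are not affected, because RRT collection is listed through Visit 9. The Day 90 endpoint is exploratory in the protocol and secondary in the SAP, outside the single primary test. The Day 14 term in the Day 90 formula is a separate and definite error. This should be corrected, but it does not threaten the trial's main conclusion.

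**What to change.** 1. Add one item to Visits 10 and 11 in Protocol 7.3, in Appendix A and in the eCRF: RRT since last visit, with dates, ongoing yes or no, and the last session before the creatinine draw.
2. In Protocol 9.2.8, extend collection of RRT status and dates to Day 90, and make 7.3, 9.2.8 and Appendix A agree.
3. In SAP 3.10.5, replace the Day 14 creatinine with the Day 90 creatinine, state all three Day 90 components, and say how a patient with unknown dialysis status is classified.
4. For patients already past Day 90, obtain the information by chart query.

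The cost is one extra question at two contacts that already take place, an eCRF field, a short SAP correction and some chart queries.
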